9.2.2 Emergency unblinding of individual subject treatment

While the safety of a subject always comes first, it is still important to carefully consider if unblinding is necessary to ensure a subject's safety. An emergency unblinding request can be made by the investigators, other HCPs who are not members of the trial staff, or authorised LEO personnel.

Provisions are in place for 24-hour emergency unblinding of individual subject treatment. If emergency unblinding is required, the investigator can unblind a subject's treatment in the IWRS. For a requester who is not a member of the trial staff and who does not have access to IWRS (e.g., a physician at an emergency room), a local contact number for the emergency unblinding contract research organisation (CRO) is provided on the subject card (see Appendix 3B) to be used if the investigator or delegated site staff cannot be reached. The requester will provide the trial ID and subject ID to the emergency unblinding CRO who will immediately reveal the individual treatment allocation.

The emergency unblinding CRO will clarify that the requester requires immediate unblinding without further medical consultation. Should the requester wish to discuss whether unblinding is necessary, the emergency unblinding CRO will provide the requester with the LEO 24/7 contact which will be diverted to the medical cover.

9.3 Background treatment (emollients)

All subjects must use an emollient twice daily (or more, as needed) for at least 14 days before randomisation; the background treatment should preferably be an additive free, basic bland emollient. On lesional skin, emollients should only be applied at times where TCS is not

Trial ID: LP0162-1339	Date: 29-Aug-2018	Version: 4.0
		Page 53 of 129

applied (i.e., emollients and TCS should not be used on the same areas at the same time of day); on TCS-untreated areas, the emollients may be applied at all times. Subjects must continue their background emollient treatment throughout the trial (including safety follow-up).

9.4 Concomitant medication and procedures

Any medication or vaccine that the subject receives from 3 months prior to screening through safety follow-up (Week 46) must be recorded in the subject's medical record and the eCRF along with details such as:

- Reason for use.
- Dates of administration including start and stop dates.
- Dosage information including dose and frequency.

Similarly, concomitant procedures (including body location, diagnosis, and start and stop date) must also be recorded in the subject's medical record and the eCRF. Note: in this trial, only surgical procedures will be recorded.

Investigators may prescribe concomitant medications or treatments to provide adequate supportive care as deemed necessary, except for medications listed in Section 9.5. The sponsor's medical expert should be contacted if there are any questions regarding concomitant or prior therapy.

Concomitant medication for conditions other than AD may be continued throughout the trial without any change in dosage whenever possible.

All subjects will receive a TCS (Europe: Class 3 [potent]; US: Class 4 [mid-strength]) for treatment of their AD from randomisation through the treatment periods (Week 0 to 32) to be used as needed based on the subject's own judgement (see Section 9.1.3.2 for details regarding dispensing of TCS [NIMP]). Low potency TCS or TCI may be used at the investigator's discretion on areas of the body where use of the supplied TCS is medically inadvisable such as areas of thin skin (face, skin fold areas, genital areas, etc.) or on areas where continued treatment is considered unsafe. Low potency TCS or TCI must be reported as concomitant medications.

Trial ID: LP0162-1339	Date: 29-Aug-2018	Version: 4.0
		Page 54 of 129

In addition, the following concomitant medications related to AD treatment are permitted from screening through safety follow-up (Week 46):

- Oral antibiotics, antiviral, or antifungal therapy for skin infections as appropriate.
- Stable doses of an emollient (see Section 9.3; subjects must apply such emollients twice daily [or more, as needed] for at least 14 days before baseline and throughout trial participation).
- Oral anti-histamines.

9.5 Prohibited medication and procedures

The following medications are prohibited during the trial from randomisation (Week 0) through Week 32:

- Use of ultraviolet A or B (UVA or UVB), psoralen + UVA (PUVA), other phototherapy, or tanning beds.
- Three or more bleach baths per week.

Any prohibited topical treatments must be recorded as concomitant medication.

The following medications are prohibited during the trial from randomisation through safety follow-up (Week 0 to 46):

- Other topical medications used for the treatment of AD other than the supplied TCS, except lower potency TCS or TCI which may be used at the investigator's discretion on areas of the body where use of the supplied TCS is not advisable.
- Investigational agents other than tralokinumab.
- Immunoglobulin or blood products.
- Systemic corticosteroids (nasal and inhaled corticosteroids are allowed).
- Systemic treatment for AD with an immunosuppressive/immunomodulating agent (e.g., cyclosporine, mycophenolate mofetil, azathioprine, methotrexate, Janus kinase inhibitors, interferon-gamma, dupilumab or other biologics).
- Allergen immunotherapy.
- Live (attenuated) vaccine.

Trial ID: LP0162-1339	Date: 29-Aug-2018	Version: 4.0
		Page 55 of 129

The sponsor's medical expert must be notified if a subject receives any of these medications during the trial.

9.6 Rescue treatment

If medically necessary (i.e., to control intolerable AD symptoms), rescue treatment for AD may be provided to trial subjects at the discretion of the investigator. If possible, investigators should attempt to limit the first step of rescue therapy to topical medications, and escalate to systemic medications only for subjects who do not respond adequately after at least 14 days of topical treatment. The subject will be monitored for signs of local or systemic TCS toxicity and the safety and appropriateness of continued use will be supervised by site staff. For reporting of AD flares see Section 10.3.1.4.

Subjects who receive topical rescue treatment (higher potency TCS: Europe Class >3; US Class <4) will continue IMP treatment.

If a subject receives rescue treatment with systemic corticosteroids or non-steroidal systemic immunosuppressive drugs (cyclosporine, methotrexate, mycophenolate-mofetil, azathioprine, etc.), IMP will be immediately discontinued (see Section 9.7.2, reasons for temporary discontinuation of IMP). After the treatment with these medications is completed, IMP may be resumed if deemed appropriate by the investigator and sponsor's medical expert, but not sooner than 5 half-lives after the last dose of systemic rescue medication.

Investigators should make every attempt to conduct efficacy and safety assessments (at least disease severity scores [IGA and EASI], concomitant medications/procedures, and AEs) immediately before administering any rescue treatment. An unscheduled visit may be used for this purpose, if necessary.

In the primary efficacy analyses, subjects who receive topical or systemic rescue treatment during the treatment periods will be considered as non-responders.

9.7 Dose modification and IMP discontinuation rules

9.7.1 Reasons for permanent discontinuation of IMP

Subjects will be permanently discontinued from IMP in the event of:

- Anaphylactic reaction or other severe systemic reaction to IMP injection.
- An AE that, in the opinion of the investigator or sponsor's medical expert, contraindicates further dosing.

Trial ID: LP0162-1339	Date: 29-Aug-2018	Version: 4.0
		Page 56 of 129

- Diagnosis of a malignancy during the trial, excluding carcinoma *in situ* of the cervix, or localised squamous or basal cell carcinoma of the skin.
- Evidence of pregnancy.
- Any infection that is opportunistic, such as active tuberculosis and other infections whose nature or course may suggest an immuno-compromised status.
- Severe laboratory abnormalities:
 - ALT and/or AST values >3×ULN with total bilirubin >2×ULN (unless elevated bilirubin is related to Gilbert-Meulengracht Syndrome).
 - O Confirmed AST and/or ALT >5×ULN (for more than 2 weeks).

Subjects who in the opinion of the subject or investigator have unacceptable treatment effect of IMP in combination with TCS therapy may discontinue treatment permanently and enter the safety follow-up period.

Refer to Section 8.5 for details on the handling of subject discontinuation and Panel 3 for assessments to be performed at an early termination visit for subjects who discontinue IMP permanently.

9.7.2 Reasons for temporary discontinuation of IMP

IMP dosing may be temporarily suspended in the event of:

- Other intercurrent illnesses or major surgery.
- An infection that requires parenteral treatment with antibiotic, antifungal, antiviral, anti-parasitic, or anti-protozoal agents.
- Treatment with systemic corticosteroids or non-steroidal immunosuppressive/immunomodulating medications (e.g., cyclosporine, methotrexate, azathioprine, mycophenolate-mofetil, Janus kinase inhibitors, dupilumab or other biologics). IMP dosing may be resumed after the medication leading to suspension of IMP is discontinued; see Section 9.6 for details regarding re-initiation of IMP after discontinuation of systemic rescue treatment.

A decision to discontinue IMP temporarily or to reinstitute IMP treatment must be discussed with sponsor's medical expert. However, the investigator may suspend trial treatment at any

Trial ID: LP0162-1339	Date: 29-Aug-2018	Version: 4.0
		Page 57 of 129

time, even without consultation with sponsor's medical expert if the urgency of the situation requires immediate action and if this is determined to be in the subject's best interest. In such cases, sponsor's medical expert should be informed as soon as possible.

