In this trial in adult subjects with moderate-to-severe AD who are otherwise healthy, the efficacy of tralokinumab in combination with TCS therapy will be compared with a placebo control group on TCS therapy. The choice of placebo (on the background of TCS) as control is appropriate for addressing the objectives of this trial and it will provide information regarding treatment with tralokinumab in combination with TCS. Subjects will be under supervision by a dermatologist or allergist every second week for the duration of the treatment period, which is more frequent than standard clinical practice. All subjects will be treated with TCS (Europe: Class 3 [potent]; US: Class 4 [mid-strength]) as needed, and rescue treatment may be given to the subjects at the investigator's discretion for the duration of the trial. Moreover, 67% of the subjects will be randomised to treatment with tralokinumab in the initial treatment period, and except for those with a clinical response in the placebo group at Week 16, all subjects will be treated with tralokinumab in the continuation period with a potential effect and benefit for the individual subject. This will ensure that the subject's AD is carefully monitored and treated as needed in this trial. If subjects are rescued with systemic corticosteroids or nonsteroid immunosuppressants they must discontinue IMP but may be eligible to restart IMP after discontinuing such rescue treatment.

Altogether, the risks associated with participating in this clinical trial are considered very low and outweighed by the benefit of a potential future treatment option for moderate-to-severe AD.

In accordance with the current version of the International Council for Harmonisation (ICH) Good Clinical Practice (GCP) guidelines, qualified medical personnel employed by LEO will be readily available to advise on trial-related medical questions. Medical monitoring will be performed throughout the trial and safety data will be reviewed regularly by medically qualified staff at LEO to ensure that prompt action is taken, if needed, to maximise patient safety.

In conclusion, the trial design chosen for this efficacy and safety trial on tralokinumab in combination with TCS therapy is regarded as ethically justified and adherent with ethical requirements.

Trial ID: LP0162-1339	Date: 29-Aug-2018	Version: 4.0
		Page 32 of 129

6 Trial objectives and endpoints

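### Section 9.7.2 makes stopping IMP on systemic rescue optional, while Sections 9.6 and 5.6 require it

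*Protocol*

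**What the plan says.** Three sections of the protocol deal with the same event.

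- **Section 9.6 (Rescue treatment).** The trigger is "If a subject receives rescue treatment with systemic corticosteroids or non-steroidal systemic immunosuppressive drugs", followed by an open-ended list of examples. The consequence is "IMP will be immediately discontinued (see Section 9.7.2, reasons for temporary discontinuation of IMP".
- **Section 5.6 (Ethical considerations).** "If subjects are rescued with systemic corticosteroids or nonsteroid immunosuppressants they must discontinue IMP but may be eligible to restart IMP" once the rescue drug has been stopped. It gives no timing for the stop.
- **Section 9.7.2 (Reasons for temporary discontinuation of IMP).** The list opens with "IMP dosing may be temporarily suspended in the event of". One listed event is "Treatment with systemic corticosteroids or non-steroidal immunosuppressive/immunomodulating medications", again with open-ended examples. The same bullet allows IMP to be resumed once the other drug has been stopped, and adds "see Section 9.6 for details regarding re-initiation of IMP after discontinuation of systemic rescue treatment". After the list comes "A decision to discontinue IMP temporarily or to reinstitute IMP treatment must be discussed with sponsor's medical expert". An exception lets the investigator suspend IMP first and inform the expert afterwards, if urgency demands it and it is in the subject's interest.

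**The concern.** Whether IMP is interrupted when a subject receives systemic immunosuppression is a subject-protection instruction. Section 5.6 also relies on it in its ethical case for the trial. Two sections state it as an obligation. The section that one of them cites for the stop states it as an option and attaches a consultation step. With approximately 70 sites (Section 7.2), different readings are plausible. Subjects in the same situation could then be handled differently from site to site, and each site could point to a protocol section in support.

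**Working it through.** The point rests on no numerical input, so there is no figure to reproduce. The check is a comparison of the texts.

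**1. Is it the same event?** Section 9.6 defines the event by purpose (rescue for AD) and drug class. Section 9.7.2 defines it by drug class alone, for any indication. Every rescue with a systemic corticosteroid or systemic immunosuppressant under Section 9.6 therefore also falls under the Section 9.7.2 bullet, and that bullet mentions systemic rescue when it points back to Section 9.6. The sections do not describe separate situations.

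**2. What does each section oblige the site to do?**

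| | Section 9.6 | Section 5.6 | Section 9.7.2 |
|---|---|---|---|
| Stop IMP | required | required | permitted |
| Timing | immediate | not stated | not stated |
| Contact with medical expert about the stop | not mentioned | not mentioned | required, with an urgency exception |

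**3. Could the permissive verb be loose drafting?** The neighbouring text suggests otherwise. Section 9.7.1 uses mandatory wording for permanent discontinuation, and Section 9.6 uses mandatory wording for continuing IMP after topical rescue. Against that usage, *may* in Section 9.7.2 reads as discretion. The urgency exception is also worded as a permission.

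**4. Do the cross-references settle it?** No. Section 9.6 sends the reader to Section 9.7.2 for the stop. Section 9.7.2 sends the reader back to Section 9.6 only for re-initiation, so the obligation to stop is never carried into Section 9.7.2. No section says which prevails.

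**5. Which site actions comply?**

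| Site action on systemic rescue | Section 9.6 | Section 5.6 | Section 9.7.2 |
|---|---|---|---|
| Stops at once and discusses with the expert | complies | complies | complies |
| Waits for the discussion before stopping | conflicts | no timing given | complies |
| Discusses and continues dosing | conflicts | conflicts | complies |

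The conflict lies in the second and third rows.

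**6. Which analyses can be affected?** Section 12.3.5 names two event types: start of rescue medication and permanent discontinuation of IMP. A temporary interruption is neither.

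- *Composite estimand (Section 12.3.5.1):* a subject rescued before the Week 16 visit is a non-responder whether or not IMP was stopped.
- *Hypothetical estimands (Sections 12.3.5.2 and 12.3.6.1):* data after the start of rescue are not used, whether or not IMP was stopped.
- *Confirmatory sequence (Section 12.3.4):* IGA 0/1, EASI75 and the pruritus responder endpoint use the composite approach, and SCORAD and DLQI use the hypothetical one. A rescued subject therefore enters all five tests in the same way under either practice.
- *Treatment-policy estimands (Sections 12.3.5.3 and 12.3.6.2):* Week 16 values after rescue are used as observed, so they may depend on whether dosing continued.
- *Exposure, adverse events and trough concentrations (Sections 12.3.3.1, 12.3.9.1 and 12.3.9.4):* these can also depend on it.

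**The case against.** The strongest reply is that the specific rule governs the general one. Section 9.6 is the dedicated rescue section. Section 9.7.2 is a general list in which one verb covers unlike events: intercurrent illness, surgery, infections needing parenteral treatment, and systemic drugs for any indication. On that reading, the pointer from Section 9.6 to Section 9.7.2 only classes the stop as temporary rather than permanent. This is a natural reading, but no section states it, and the Section 9.7.2 bullet mentions systemic rescue without exempting it from the permissive verb.

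Second, the consultation conflict is limited. Section 9.7.2 does not say that the discussion must come before the stop, and it allows for urgency. Section 9.5 separately requires the medical expert to be notified when a prohibited systemic drug is given. IMP is given only at site visits every 2 weeks, so contact will often be possible before the next dose. All of this makes unnoticed divergence less likely. None of it makes the stop mandatory under Section 9.7.2.

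Third, the treatment-policy estimands are defined regardless of rescue and discontinuation, and they are supportive. That is correct, and it keeps the statistical consequence small.

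**Conclusion.** The inconsistency is real and stands in the current text: for systemic rescue, stopping IMP is mandatory in Sections 9.6 and 5.6 and optional in Section 9.7.2. It matters mainly for subject protection. The data consequence is confined to exposure, safety, PK and possibly treatment-policy results. The confirmatory Week 16 tests are not affected. Divergence in practice also assumes that some site reads Section 9.7.2 as governing systemic rescue.

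A reader might infer more than the documents support:

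- *That the rules are opposite.* Section 9.7.2 permits a stop and nowhere tells a site to continue. The contrast is mandatory versus optional.
- *That Section 5.6 also demands an immediate stop.* Only Section 9.6 gives that timing.
- *That the drug lists contradict each other.* Section 9.7.2 names Janus kinase inhibitors and biologics and Section 9.6 does not, but both lists are illustrative and Section 9.7.2 is not limited to rescue.
- *That Section 9.6 is meant to prevent concurrent exposure to IMP and systemic immunosuppression.* It gives no reason for the stop.
- *That the number of subjects can be estimated.* The documents give no rate of systemic rescue. An assumed 2% to 5% of the 369 randomised subjects gives 0.02 × 369 ≈ 7 to 0.05 × 369 ≈ 18. That range has no basis in the protocol, and it counts everyone rescued systemically rather than those whose site departs from Section 9.6. The point does not depend on it.

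**What to change.** Reconcile Sections 5.6, 9.6 and 9.7.2 so that they state one rule for systemic rescue: whether interruption of IMP is required, and how it is timed relative to contact with the sponsor's medical expert. In Section 9.7.2, take systemic rescue out of the shared list, or mark it as a separate case, so that the verb chosen for the other events does not govern it. Which rule applies is for the sponsor's clinicians to decide, and no view on that is offered here.

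The cost is wording in up to three sections, with whatever approval Appendix 3A requires for an amendment. No analysis, sample size or data collection changes.

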9.8 Treatment logistics and accountability

9.8.1 Labelling and packaging of trial products

9.8.1.1 Labelling and packaging of IMPs

The IMP will be packaged in individually numbered kits, each containing 1 syringe (tralokinumab 150 mg or placebo).

Primary and secondary packaging materials (syringe and outer carton, respectively) will be individually labelled.

The labelling of IMPs will be in accordance with Annex 13, local regulations, and trial requirements. Label text will be translated into local languages, as required. The inner label will be in English for kits used at trial sites.

9.8.1.2 Labelling and packaging of NIMP

The NIMP (TCS) will be packaged in individually numbered kits that contain tubes of TCS cream with a total weight of 180–225 g.

Primary and secondary packaging materials (tube and outer kit carton, respectively) will be individually labelled.

The labelling of NIMPs will be in accordance with Annex 13, local regulations, and trial requirements. Label text will be translated into local languages, as required. The inner label will be in English for kits used at trial sites.

9.8.2 Storage of trial products

9.8.2.1 Storage of IMPs

All LEO supplied IMPs must be stored in a secure and restricted area under the conditions specified on the label and remain in the original container until dispensed.

The IMP must be stored at 2 to 8°C at the site. The temperature during storage must be monitored by a calibrated, stationary, and continuously monitoring system. Minimum requirement is a calibrated min/max thermometer.

Trial ID: LP0162-1339	Date: 29-Aug-2018	Version: 4.0
		Page 58 of 129

A temperature log must be kept to document the storage within the right temperature interval. Storage facilities should be checked at least every working day.

Storage of IMP may be delegated, e.g. to a hospital pharmacy, as locally applicable.

Note that in the cases listed below, site staff should not use the affected IMP and should immediately contact their CRA for further guidance:

- Temperature excursion upon receipt or during storage at the trial site.
- Damaged kit upon receipt.
- Damaged syringe/cartridge.

Damaged IMP should be documented via IWRS (refer to the IWRS instructions for further details) and reported as a product complaint to Global Pharmacovigilance, LEO (see Section 9.10). Damaged IMP should not be used.

9.8.2.2 Storage of NIMP

All LEO supplied NIMP (TCS) must be stored in a secure and restricted area under the conditions specified on the label and remain in the original container until dispensed.

The NIMP must be stored at room temperature at the site according to the approved local label for mometasone furoate. The temperature during storage must be monitored by a calibrated, stationary, and continuously monitoring system. Minimum requirement is a calibrated min/max thermometer.

A temperature log must be kept to document the storage within the right temperature interval. Storage facilities should be checked at least every working day.

Storage of NIMP may be delegated, e.g. to a hospital pharmacy, as locally applicable.

Note that in the cases listed below, site staff should not use the affected NIMP and should immediately contact their CRA for further guidance:

- Temperature excursion upon receipt or during storage at the trial site.
- Damaged kit upon receipt.

Damaged NIMP should be documented via IWRS (refer to the IWRS instructions for further details) and reported as a product complaint to Global Pharmacovigilance, LEO (see Section 9.10). Damaged NIMP should not be used.

Trial ID: LP0162-1339	Date: 29-Aug-2018	Version: 4.0
		Page 59 of 129

